2.3.2 Risks

Full details regarding tolerability and safety of Gamunex-C are provided in the prescribing information and the IB. The main risks of Gamunex-C are summarized below:

- Gamunex-C is contraindicated in subjects with a known history of anaphylactic or severe systemic reaction to human immunoglobulins, especially in subjects with antibodies against IgA.

GRIFOLS	Number	BLG-CL-PRT-000020	Version	4.0	Status	Effective	Effective Date	19-Jul-2021
	GC2007 - A Multicenter, Randomized, Open-label Parallel Group Pilot Study to Evaluate Safety and Efficacy of High Dose Intravenous Immune Globulin (IVIG) plus Standard Medical Treatment (SMT) versus SMT alone in Bioscience Industrial Group						Page	25 of 91

- Certain adverse events may be related to the rate of infusion. Subjects must be closely monitored and carefully observed for any symptoms throughout the infusion period.
- There is clinical evidence of an association between IVIG administration and thromboembolic events such as myocardial infarction, cerebral vascular accident (including stroke), PE, and DVT that is assumed to be related to a relative increase in blood viscosity through the high influx of immunoglobulin in at-risk subjects. In subjects at risk for thromboembolic ARs, IVIG products should be administered at the minimum rate of infusion and dose practicable.
- Cases of acute renal failure have been reported in subjects receiving IVIG therapy. In most cases, risk factors have been identified, such as pre-existing renal insufficiency, diabetes mellitus, hypovolemia, overweight, concomitant nephrotoxic medicinal products, or age over 65. In subjects at risk for acute renal failure, IVIG products should be administered at the minimum rate of infusion and dose practicable.
- Aseptic meningitis syndrome (AMS) has been reported to occur in association with IVIG treatment. Discontinuation of IVIG treatment has resulted in remission of AMS within several days without sequelae.
- Gamunex-C may contain blood group antibodies which may act as hemolysins and induce in vivo coating of red blood cells with immunoglobulin, causing a positive direct antiglobulin reaction (Coombs test) and, rarely, hemolysis. Hemolytic anemia can develop subsequent to IVIG therapy due to enhanced red blood cells sequestration. IVIG recipients should be monitored for clinical signs and symptoms of hemolysis. If these are present after IVIG infusion, perform appropriate confirmatory laboratory testing.

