5.3.2 Removal of Subjects

Subjects may withdraw or be withdrawn from the study for the following reasons:

1. At their own request or at the request of their legally acceptable representative.
2. If, in the investigator's opinion, continuation in the study would be detrimental to the subject's well-being.
3. At the specific request of the sponsor.

GRIFOLS Bioscience Industrial Group	Number	BLG-CL-PRT-000020	Version	4.0	Status	Effective	Effective Date	19-Jul-2021	Page	43 of 91
	GC2007 - A Multicenter, Randomized, Open-label Parallel Group Pilot Study to Evaluate Safety and Efficacy of High Dose Intravenous Immune Globulin (IVIG) plus Standard Medical Treatment (SMT) versus SMT alone in									

Also, subjects may be withdrawn for the following reasons:

1. The subject is not able to adhere to the main protocol requirements (major protocol violations).
2. The occurrence of an AE which in the investigator's opinion requires the withdrawal of the subject from the clinical trial.
3. The subject is lost to follow-up.
4. Subject's death.
5. Any event which in the opinion of the investigator impedes the subject's participation in the study.

With regard to individual subject criteria for discontinuation of Gamunex-C IV infusions, discontinuation of study drug treatment will occur if the subject develops any of the following:

- Evidence of hypersensitivity/anaphylaxis to Gamunex-C
- Occurrence of thromboembolic complication (e.g., pulmonary embolism) whether or not related to COVID-19
- Hypertensive emergency with sustained systolic blood pressure > 200 mm Hg unresponsive to intervention or refractory severe hypotension with sustained systolic blood pressure < 90 mm Hg unresponsive to vasopressors
- Development of renal failure with creatinine ≥ 4 mg/dL (or subject becomes dependent on dialysis/renal replacement therapy)

In all cases, the reason for withdrawal must be recorded in the study record and in the subject's records.

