8.3.8 Adverse Event Documentation

All AEs and SAEs occurring on Day 1 through the Day 29 (± 1 day)/Final Visit must be fully recorded in the subject’s medical record and CRF, and SAE form (if serious).

At the time of the Day 60 (± 2 days) and Day 90 (± 2 days) Phone Checks any additional SAEs/non-serious AEs will also be collected and recorded.

It is the responsibility of the investigator to ensure that AEs are appropriately recorded.

AEs will be collected through directly observed events or spontaneously volunteered by the subject. Clearly related signs, symptoms and abnormal diagnostic procedures should preferably be grouped together and recorded as a single diagnosis or syndrome wherever possible.

The following variables must be recorded:

- The verbatim term (a diagnosis is preferred)
- Date/time of onset
- Date/time of resolution
- Severity (mild, moderate, severe [Grade 3 to Grade 5])
- Causality (unrelated, possibly related, definitely related)*
- Seriousness (yes, no)
- Action taken (with regard to IP)
- Other action (to treat the event)
- Outcome and sequel (follow-up on AE)

*Causality assessment will be made only when the AE occurs after the subject has initiated at least one infusion of the IP. An AE occurring before subject’s exposure to IP will be always labeled as “unrelated”.

GRIFOLS Bioscience Industrial Group	Number	BlG-CL-PRT-000020	Version	4.0	Status	Effective	Effective Date	19-Jul-2021	Page	61 of 91
	GC2007 - A Multicenter, Randomized, Open-label Parallel Group Pilot Study to Evaluate Safety and Efficacy of High Dose Intravenous Immune Globulin (IVIG) plus Standard Medical Treatment (SMT) versus SMT alone in									

For AEs that occur during infusions, the infusion rate in effect at the time of onset of the AE, the time of onset of the AE and the time of AE change materially in intensity and/or resolve will be captured.

In addition to the investigator's own description of the AE, each AE will be encoded according to the Medical Dictionary for Regulatory Activities (MedDRA).

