#### 2.1.4 Safety Objective

To determine the safety and tolerability profile through Day 29 of high dose IVIG plus SMT versus SMT alone in hospitalized subjects with COVID-19.

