## 7. SAFETY ANALYSIS

Safety assessments will include assessment of AEs, chemistry, hematology (complete blood count and differential), COVID-19 clinical features, vital signs, and hospital interventions. All safety summaries (or analyses if applicable) will be conducted using the SAF population. No formal hypothesis testing will be performed to compare differences between treatment groups.

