## 7.2.5 Adverse Event Summaries

All AEs (serious and non-serious) occurring after randomization and before the end of study, regardless of relationship to IP, will be included and classified by SOC and PT using MedDRA.

For TEAEs, the following will be summarized and presented for the SAF population:

- i. An overall summary of TEAEs, which includes:
  - a. the number and percentage of subjects experiencing a TEAE
  - b. the number and percentage of subjects experiencing a TEAE by strongest relationship to IP
  - c. the number and percentage of subjects experiencing a TEAE by greatest severity
  - d. the number and percentage of subjects experiencing a TEAE with Grade  $\geq 3$
  - e. the number and percentage of subjects experiencing a treatment-emergent SAE
  - f. the number and percentage of subjects experiencing a TEAE leading to death
  - g. the number and percentage of subjects experiencing a TEAE leading to study withdrawal
- ii. the number and percentage of subjects experiencing a TEAE by SOC and PT.
- iii. the number and percentage of subjects experiencing an adverse drug reaction (ADR; i.e., potentially related TEAE) by SOC and PT, where an ADR is defined as any TEAE with a causal relationship to IP assessed as 'Possibly Related' or 'Definitely Related'.
- iv. the number and percentage of subjects experiencing a TEAE by SOC, PT and the strongest relationship to IP
- v. the number and percentage of subjects experiencing a TEAE by SOC, PT and the greatest severity
- vi. the number and percentage of subjects experiencing a TEAE with Grade  $\geq 3$  by SOC and PT
- vii. the number and percentage of subjects experiencing an ADR with Grade  $\geq 3$  by SOC and PT
- viii. the number and percentage of subjects experiencing a treatment-emergent SAE by SOC and PT
- ix. the number and percentage of subjects experiencing a potentially related treatment-

- emergent SAE by SOC and PT
- x. the number and percentage of subjects experiencing a TEAE leading to death by SOC and PT
- xi. the number and percentage of subjects experiencing a TEAE leading to study withdrawal by SOC and PT

In the overall summary of TEAEs table (i), besides tabulating the number and percentage of subjects, the total number of TEAE episodes will also be provided. If a subject has repeated episodes of a particular TEAE, all episodes will be counted in the summary table.

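### The SAP tabulates TEAEs leading to study withdrawal but not TEAEs that stop or interrupt Gamunex-C, and never groups the named IVIG risks by arm, so the comparative safety objective is incompletely answered

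*SAP*

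**What the plan says.** The safety objective (SAP 2.1.4) is comparative: "To determine the safety and tolerability profile through Day 29 of high dose IVIG plus SMT versus SMT alone".

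SAP 7.2.5 lists the TEAE tables: overall, by relationship, by severity, Grade 3 or higher, adverse drug reactions, SAEs and TEAEs leading to death. For discontinuation it has item i.g in the overall table, "the number and percentage of subjects experiencing a TEAE leading to study withdrawal", and item xi, "the number and percentage of subjects experiencing a TEAE leading to study withdrawal by SOC and PT". Action taken with regard to IP is one of the fields in the by-subject AE listing and in no table.

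Protocol 5.3.2 treats two things separately. Reasons for leaving the study include "Subject's death". For the infusions it says that "discontinuation of study drug treatment will occur if the subject develops any of the following", followed by hypersensitivity, thromboembolic complication, a blood pressure event and renal failure. Protocol 8.3.8 requires the action taken on IP to be recorded for each AE.

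Protocol 2.3.2 names the main risks and states: "There is clinical evidence of an association between IVIG administration and thromboembolic events". The examples are myocardial infarction, stroke, pulmonary embolism and deep vein thrombosis. SAP 7.2.5 classifies events by system organ class and preferred term and defines no grouped term. SAP 7 adds: "No formal hypothesis testing will be performed to compare differences between treatment groups".

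**The concern.** Tolerability of an infused product is usually read from the events that caused it to be stopped or interrupted. The plan collects that information but does not tabulate it. It tabulates study withdrawal instead, which is a different event and in an ICU trial may partly duplicate the deaths.

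The named thromboembolic risk is several different diagnoses. Shown only by class and term, a modest excess could sit on several lines of one to three subjects each. The relationship and adverse drug reaction tables cannot supply the comparison between arms, because Protocol 8.3.8 has causality assessed only once a subject has started an infusion. SMT-arm events therefore have no counterpart in those tables.

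At stake is whether the final tables let a reader see how often Gamunex-C was stopped for an adverse event, and whether the main named risk was more frequent with IVIG.

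**Working it through.** The documents give no safety rate, power or safety sample size, so there is no stated figure to reproduce. The first check is textual. The rest is illustration at 50 per arm (about 100 randomized 1:1), and every rate is an assumption.

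**1. Where a drug-stopping TEAE appears**

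| Output | Shows the event? | Shows that it stopped Gamunex-C? |
|---|---|---|
| SAP 7.2.5, TEAE tables by class and term | Yes | No |
| SAP 7.2.5, i.g and xi | Only if the subject also left the study | No |
| SAP 7.2.5, AE listing | Yes | Yes, subject by subject |
| SAP 7.1, interruption and whether 100% infused | No | Not linked to a TEAE |

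Protocol 6.1 allows an infusion to be stopped for extravasation, so the SAP 7.1 interruption count mixes toxicity with line problems. The compliance formula divides volume infused by volume prepared. With the protocol's example of 280 mL a day for 5 days, a subject stopped after two infusions scores 560/560 = 100% if only two were prepared. Against the planned course the figure is 560/1400 = 40%.

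If 5% to 20% of IVIG subjects stop for a TEAE, the expected number is 50 × 0.05 = 2.5 to 50 × 0.20 = 10. At 5%, the chance of at least one is 1 − 0.95^50 = 92%.

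**2. Deaths in the withdrawal rows, if every fatal TEAE carries the withdrawal flag**

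Share of deaths = 50m / (50m + 50w), where m is Day 29 mortality and w is non-fatal withdrawal for a TEAE.
- m = 20%, w = 5%: 10/12.5 = 80%
- m = 40%, w = 2%: 20/21 = 95%

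This range is conditional. The documents do not say how the flag is set.

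**3. Grouped event against separate classes**

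The interval is Newcombe's 95% interval for a risk difference, built from the Wilson limits (l, u) of each arm: lower = d − √[(p1 − l1)² + (u2 − p2)²], upper = d + √[(u1 − p1)² + (p2 − l2)²].

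One worked case: 13/50 v 5/50.
- Wilson limits are 0.159 to 0.396 and 0.043 to 0.214, and d = 0.16.
- Lower = 0.16 − √(0.101² + 0.114²) = 0.008; upper = 0.16 + √(0.136² + 0.057²) = 0.307.
- The same events split 4, 3, 3, 3 v 2, 1, 1, 1 give 0.04 (−0.066 to 0.152) for the 4 v 2 class and 0.04 (−0.054 to 0.143) for each 3 v 1 class.

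The grouped interval excludes zero and no single class does.

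Over 200,000 simulated trials per scenario, with each affected subject in one class, the percentage of trials whose interval excludes zero is:

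| SMT v IVIG risk | Split over four classes | Grouped | Any single class |
|---|---|---|---|
| 10% v 15% | even | 10% | 5% |
| 10% v 20% | even | 27% | 13% |
| 10% v 25% | even | 50% | 26% |
| 10% v 25% | 70% in one class | 50% | 34% |
| 10% v 30% | even | 72% | 42% |

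**The case against.** Much of the case on the other side stands.

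- A reader might infer that stopping for toxicity is not measured. It is measured: action on IP is recorded and listed, and SAP 7.1 summarises doses received, interruptions and incomplete infusions. What is missing is the tabulation that joins the two.
- A reader might infer that the stopping events themselves are lost. They still count in the TEAE tables by class and term and, where they qualify, in the Grade 3 or higher, SAE and adverse drug reaction tables.
- A reader might infer that the withdrawal rows will fill with deaths. That rests on 5.3.2 alone. Outcome and study withdrawal are separate listing fields, fatal TEAEs have their own rows (i.f and x), and SAP 5.1 tabulates reasons for early termination by arm, so any deaths included could be identified.
- The event types in the three stated safety endpoints are all tabulated, and the laboratory summaries in SAP 7.3 partly cover renal failure and haemolysis.
- The illustrated excesses may be too large. Protocol 2.2 describes thromboembolic reactions to IVIG as very rare, and the exclusion criteria remove high-risk subjects. Smaller excesses would usually be missed even when grouped, and the gain shrinks when one class dominates.

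The remaining argument is that safety is descriptive by design. That does not answer the point: a risk difference with an interval is estimation and needs no test. Nor do the existing tables give the by-arm comparison, regardless of causality, for a risk made up of several diagnoses.

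**Conclusion.** The point holds as an incompleteness in the safety tables. SAP 7.2.5 does not tabulate TEAEs that stop or interrupt Gamunex-C, does not say whether fatal TEAEs enter the withdrawal rows, and gives no grouped between-arm estimate for the named risks. The documents do not support a stronger conclusion that the safety objective goes unanswered or that the data are missing.

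For excesses of 5 to 20 percentage points over an assumed 10%, with an even four-way split, grouping raises the chance that the interval excludes zero by about 5 to 30 percentage points. The result depends on the assumed rates, on 50 per arm and on how events fall across classes. The documents do not give that placement. The death share of 80% to 95% depends further on an unstated eCRF rule.

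**What to change.** Change SAP 7.2.5 only.

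1. Add, for the IVIG arm, the number and percentage of subjects with a TEAE leading to permanent discontinuation of Gamunex-C, and separately to its interruption, overall and by class and term. Take these from the recorded action on IP. The documents do not show that field's response options; if they do not separate the two, use the infusion records as well.
2. Keep items i.g and xi for both arms, but show withdrawals excluding fatal TEAEs. The new rows exist in one arm only, so they cannot replace a two-arm row.
3. Add one table by arm, regardless of causality, of grouped terms for the named risks. Put thromboembolic events first, then acute renal failure, haemolysis, aseptic meningitis and hypersensitivity or anaphylaxis. Show acute lung injury with a note that COVID-19 symptoms are not recorded as TEAEs unless IVIG is suspected. Give the risk difference with its 95% interval, labelled as estimation and not as a test. Fix the term lists before database lock, since the trial is open-label.

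The cost is one or two more tables and a term list to agree. AEs and action on IP are already recorded, and no stopping or withdrawal rule changes.

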### 7.3 Clinical Laboratory Assessments

Clinical laboratory tests will be obtained at the time points presented in Appendix A. Continuous clinical laboratory values will be summarized by presenting descriptive statistics of raw data and change from baseline values at each time point for each treatment group, if feasible. If necessary, quantitative lab values reported in different units for the same lab parameter will be converted to the same units prior to being summarized. Qualitative results at each time point measured will be summarized by presenting the number and percentage of subjects for each category. Shift tables, based on the high/low flags, will also be summarized by treatment group at each visit for all laboratory tests with normal ranges, when available.

Laboratory parameter results from unscheduled visits will be excluded from table summaries but will be included in data listings. When there are repeat scheduled measurements for a given visit, only the last measurement will be used in the table summaries.

Listings will include flags for values outside of the reference ranges, when available, and clinical significance if a laboratory result is deemed abnormal when applicable.

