10. Known history of prothrombin gene mutation 20210, homozygous Factor V Leiden mutations, antithrombin III deficiency, protein C deficiency, protein S deficiency or antiphospholipid syndrome.
11. Presence of malignancy (either new diagnosis of malignancy or known residual disease) within the past 12 months (note: exceptions for non-melanoma skin cancer and carcinoma in situ of cervix are allowed)
12. Creatinine at Screening is \geq 4 mg/dL (or subject is dependent on dialysis/renal replacement therapy)
13. Known Immunoglobulin A (IgA) deficiency with anti-IgA serum antibodies
14. Uncontrolled hypertension at the time of Screening (systolic blood pressure $>$ 200 mm Hg) or refractory severe hypotension with sustained systolic blood pressure $<$ 90 mm Hg unresponsive to vasopressors.

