8.3.1 Warnings/Precautions

True hypersensitivity reactions from IVIG administration are rare. They can occur in subjects with anti-IgA antibodies. Rarely, human normal immunoglobulin can induce a fall in blood pressure with anaphylactic reaction, even in subjects who had tolerated previous treatment with human normal immunoglobulin.

There is clinical evidence of an association between IVIG administration and thromboembolic events such as myocardial infarction, cerebral vascular accident (including stroke), PE, and DVT that is assumed to be related to a relative increase in blood viscosity through the high influx of immunoglobulin in at-risk subjects. In subjects at risk for thromboembolic adverse reactions, IVIG products should be administered at the minimum rate of infusion and dose practicable.

Cases of acute renal failure have been reported in subjects receiving IVIG therapy. In most cases, risk factors have been identified, such as pre-existing renal insufficiency, diabetes mellitus, hypovolemia, overweight, concomitant nephrotoxic medicinal products, or age over 65. In case of renal impairment, IVIG discontinuation should be considered. While these reports of renal dysfunction and acute renal failure have been associated with the use of many of the licensed IVIG products containing various excipients such as sucrose, glucose, and maltose, those containing sucrose as a stabilizer accounted for a disproportionate share of the total number. In subjects at risk, the use of IVIG products that do not contain these excipients may be considered. Gamunex-C *does not* contain sucrose, maltose, or glucose.

AMS has been reported to occur in association with IVIG treatment. The syndrome usually begins within several hours to 2 days following IVIG treatment.

Gamunex-C may contain blood group antibodies which may act as hemolysins and induce in vivo coating of red blood cells with immunoglobulin, causing a positive DAT and, rarely, hemolysis. Hemolytic anemia can develop subsequent to IVIG therapy due to enhanced red blood cells sequestration. IVIG recipients should be monitored for clinical signs and symptoms of hemolysis. If these are present after IVIG infusion, perform appropriate confirmatory laboratory testing.

In subjects receiving IVIG, there have been some reports of acute non-cardiogenic pulmonary oedema (Transfusion Related Acute Lung Injury [TRALI]). TRALI is characterized by severe hypoxia, dyspnoea, tachypnoea, cyanosis, fever and hypotension.

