## 4. GENERAL CONSIDERATIONS FOR DATA ANALYSIS

Unless otherwise specified, continuous variables will be summarized using descriptive statistics (n, mean, standard deviation, median, minimum, and maximum). Categorical variables will be summarized showing the number and percentage of subjects within each category.

Summary results will be provided for each treatment group. All tabulations will be based on pooled data across centers.

All statistical tests will be two-sided and tested at the 5% level of significance.

Analyses will be performed using SAS for Windows statistical software, version 9.4 or higher (SAS, Cary, NC), except where other software may be deemed more appropriate. In the event that other software is used to perform some analyses, the details will be provided in the Clinical Study Report.

■ will perform all efficacy and safety analyses described in this SAP.

Subject data will be listed, sorted by treatment group and subject number. When applicable, listings will be additionally sorted by visit and assessment date/time.

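### Laboratory shift tables based on high/low flags, with unscheduled results left out, do not count subjects whose creatinine or haemoglobin worsened from an abnormal baseline or whose DAT converted

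*SAP*

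**What the plan says.** SAP Section 7.3 sets out the laboratory summaries:

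- **Shift tables.** "Shift tables, based on the high/low flags, will also be summarized by treatment group at each visit for all laboratory tests with normal ranges", where such ranges are available. The only basis is the flag. No table uses a toxicity grade, a relative change or the worst post-baseline value.
- **Continuous tests.** "Continuous clinical laboratory values will be summarized by presenting descriptive statistics of raw data and change from baseline values at each time point", by arm where feasible. SAP Section 4 defines the statistics as "n, mean, standard deviation, median, minimum, and maximum".
- **Qualitative tests.** "Qualitative results at each time point measured will be summarized by presenting the number and percentage of subjects for each category". The text of 7.3 does not name the DAT, but SAP Appendix A schedules it on Days 1, 5, 15 and 29. For a positive/negative result, this is the rule that applies.
- **Unscheduled results.** "Laboratory parameter results from unscheduled visits will be excluded from table summaries but will be included in data listings". If a scheduled test is repeated within a visit, only the last value is tabulated.
- **Listings.** Out-of-range values are flagged, with clinical significance where applicable.

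SAP Section 8 applies the same methods to the safety interim after 50 subjects.

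The protocol names the relevant risks. Section 2.3.2 says "Cases of acute renal failure have been reported in subjects receiving IVIG therapy" and lists existing renal insufficiency among the risk factors. Section 8.3.1 says that blood group antibodies in the product may coat red cells, "causing a positive DAT and, rarely, hemolysis". Exclusion criterion 12 in Section 5.2 bars entry on creatinine only from 4 mg/dL upwards, or with dialysis dependence.

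**The concern.** A shift table is where a safety reader looks for the number of subjects per arm who got worse. A high/low flag has one level on each side of the normal range, so a subject who starts above the limit cannot move further up, and one who starts below cannot move further down. Eligibility admits subjects with raised creatinine, and nothing in it excludes a low haemoglobin. In those subjects, worsening in the expected direction registers as no change, while a small crossing of the limit in another subject registers as a shift.

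The DAT is collected because immunoglobulin can turn it positive. Per-visit percentages mix subjects who were positive at entry with those who converted.

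What is at stake is an objective by-arm count for two harms that the protocol itself names, at the final analysis and at an interim with about 25 subjects per arm. The protocol already works with such counts: several suspension criteria in Section 8.5 are numbers of subjects at a given CTCAE grade.

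**Working it through.** The documents state no figure on this point, so there is nothing to reproduce. The checks below are illustrations.

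**1. What the flag can register.** The documents give no reference range for creatinine. I assume upper limits of 1.0, 1.2 and 1.4 mg/dL; the zero band of the SOFA creatinine item in Protocol Appendix 4 ends at 1.2. Rule: High if the value exceeds the limit. All three limits give the same flags.

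| Creatinine, mg/dL | Flag shift | Ratio | SOFA creatinine points |
|---|---|---|---|
| 0.9 to 2.0 | Normal to High | 2.22 | 0 to 2 |
| 1.5 to 3.0 | High to High | 2.00 | 1 to 2 |
| 1.5 to 3.9 | High to High | 2.60 | 1 to 3 |
| 2.0 to 3.9 | High to High | 1.95 | 2 to 3 |
| 3.9 to 6.0 | High to High | 1.54 | 3 to 4 |

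All four High to High pairs cross at least one SOFA band, so the protocol's own scale separates values that the flag merges. Low to Low haemoglobin behaves in the same way.

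**2. What the change-from-baseline table adds.** Let k of n subjects in an arm rise by 3.9 − 1.5 = 2.4 mg/dL and the others not change. Then mean = 2.4k/n and SD = 2.4 × √[k(n − k) / (n(n − 1))]. I use n = 50 for the final analysis and n = 25 for the interim.

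| n | k | Mean | SD | Median | Maximum |
|---|---|---|---|---|---|
| 50 | 1 | 0.048 | 0.34 | 0 | 2.4 |
| 50 | 5 | 0.24 | 0.73 | 0 | 2.4 |
| 25 | 1 | 0.096 | 0.48 | 0 | 2.4 |
| 25 | 5 | 0.48 | 0.98 | 0 | 2.4 |

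The table responds: the maximum shows that a large rise occurred, and the mean and SD grow with k. It does not print k. Once the other subjects vary in the ordinary way, k cannot be read back from these statistics.

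**3. What per-visit DAT counts determine.** Suppose n subjects are tested at both visits, a positive at baseline and b positive later. The number of negative-to-positive conversions lies between max(0, b − a) and min(b, n − a). With n = 50 and b = 10:

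- a = 0: exactly 10.
- a = 3: 7 to 10.
- a = 10: 0 to 10.

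Deaths and missed samples, which change who is counted at each visit, make the bounds looser.

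**4. Timing.** Infusions run through Day 4 or Day 5. Scheduled post-baseline samples fall on Days 5, 15 and 29, each ±1. The interval from the first to the second is 10 days nominally, and from (15 − 1) − (5 + 1) = 8 to (15 + 1) − (5 − 1) = 12 days within the windows. From Day 15 to Day 29 it is 14 days. Protocol Sections 7.2.5 and 7.2.7 allow a phone call in place of the Day 15 or Day 29 visit. A peak between visits reaches only the listings.

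**The case against.** The strongest reply is that several other outputs would show such harm.

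- **Adverse events.** Protocol Section 8.3.8 requires clinically significant laboratory abnormalities to be reported as adverse events. SAP Section 7.2.5 tabulates these as subject counts by arm, by preferred term, severity, Grade 3 or above, and seriousness. The COVID-19 symptoms exempted from recording in Protocol Section 4.1.4 do not include renal failure or haemolysis.
- **Change from baseline.** A large change at a scheduled visit appears in, or is exceeded by, the printed minimum or maximum.
- **SOFA.** The score includes graded creatinine, bilirubin and platelet items, and its change is analysed.
- **Individual data.** With about 50 subjects per arm, flagged listings can be read subject by subject, and the sponsor's safety review committee assesses causality for all treatment-emergent events.
- **DAT.** If no subject is positive at baseline and the same subjects are tested, per-visit counts give the conversions exactly.

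Most of this stands, and it limits the point. A reader might infer that the plan hides renal injury and haemolysis, or that the flag-based shift is its only categorical look at laboratory harm. The documents do not support either reading.

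The gap remains for three reasons. Whether a value becomes an adverse event depends on investigator judgement in an open-label trial, and Protocol Section 8.3.8 assesses causality only after an infusion has started, so the adverse-reaction tables have no comparable control arm. SOFA is analysed as a total, not by item. Change statistics and listings leave the counting to the reader.

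**Conclusion.** The point holds as a reporting gap. Under SAP Section 7.3, worsening from an already abnormal baseline shows as no shift, unscheduled peaks enter no table, and no laboratory table counts subjects per arm who worsened by grade or converted on the DAT.

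Its size in subjects cannot be stated. For each test it depends on the share already abnormal in the relevant direction at baseline, and for the DAT on the share already positive. The documents give neither. The illustrations rest on assumed upper limits, an assumed rise of 2.4 mg/dL and, for the DAT, a positive/negative result.

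A reader might also infer that the tables are blind in the highest-risk subjects generally. That goes too far: of the six renal risk factors in Protocol Section 2.3.2, only existing renal insufficiency itself implies an abnormal starting creatinine.

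Safety is descriptive, with no testing between arms, and the primary analysis and sample size are untouched. This is a worthwhile, inexpensive improvement. It does not threaten the trial's main conclusion.

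**What to change.** In SAP Section 7.3, and so for the interim under Section 8, add by arm:

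1. **Grade shifts.** A table of baseline CTCAE grade against worst post-baseline grade for creatinine and haemoglobin (optionally bilirubin, ALT and platelets), including unscheduled values. CTCAE is already the protocol's grading system, so no new cut-offs are needed. The documents neither give its version nor reproduce the grade limits, so the SAP should name the version and say how grades are assigned when the baseline is abnormal.
2. **The same table from scheduled visits only.** Unscheduled sampling may differ between arms, and showing both versions lets the reader judge that.
3. **DAT cross-table.** Baseline result against the result at each visit, with conversions counted among baseline-negative subjects who have a result at that visit.

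The existing high/low shift tables can stay. The cost is SAP wording and a few descriptive tables. The data are already planned for collection, although unscheduled values can be used only as far as they reach the database. A graded table still merges changes within a grade. No dosing, stopping or other clinical rule changes.
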